### **ANCILLARY STUDY BY OMRF TEAM:**

**This Summarizes an overlapping project Submitted as Hyperaccelerated R01 (April 15, 2013): [name] PI, [name], [name], [name].** The entire application is also included along with this protocol and the Investigator's Brochure as part of the IRB approval package.

**2. SPECIFIC AIMS:** Systemic lupus erythematosus (SLE) is a diverse, systemic autoimmune disease which causes significant morbidity and early mortality, especially in minority populations and in women of child-bearing age. By the time patients receive the devastating SLE diagnosis, the majority have ongoing aggressive inflammatory processes and oftentimes damage that cannot be reversed (1). Clinical trials for lupus for many potential therapies have been hampered by problematic trial designs including 1) endpoints clouded by confusion over events which do or do not have clinical consequences and 2) high placebo response rates which are driven by background use of corticosteroids and "standard of care" medication use in the placebo arms (2, 3).

Abatacept (CTLA-Ig) has been evaluated for SLE by Bristol-Myers Squibb (BMS) in moderate sized Phase II clinical trials for nephritis and non-nephritis SLE patients (4, 5). These previously completed trials failed to meet primary or secondary endpoints, but exploratory analyses suggested that the problematic clinical endpoints (referred to above) and aggressive background treatments might have impaired the interpretation of these studies. The current clinical trial "Clarification of Abatacept Effects in SLE with Integrated Biologic and Clinical Approaches (ABC) funded by Bristol-Myers Squibb (BMS) utilizes an immune suppressant withdrawal strategy coupled to endpoints which have been shown to provide maximal discriminatory capacity by minimizing the "noise" of minor improvements and clinically insignificant disease flares. This trial uses the trial design introduced in the recently completed Biomarkers of Lupus Disease (BOLD) study (6).

Abatacept was originally developed to finely target T cell costimulation by binding CD80/CD86 on antigen presenting cells (APCs), thus blocking the signals delivered to T cells through CD28 (7-9). However, abatacept likely has effects on both APCs and T cells. The

exact biologic mechanism(s) that result in improved clinical outcomes is still unclear. By partnering ancillary NIAMS funding to assess the immune activating and regulatory pathways in subjects from

the ABC Study, we create an ideal study which needs to be considered for the hyperaccelerated award mechanism. The trial design of the parent study makes these particular samples invaluable for

answering not only important questions about abatacept function, but also critical questions about mechanisms of SLE disease flare in patients off immunomodulatory drugs. Results from these studies will also provide information about additional biologic endpoints that allow for more appropriate SLE therapeutic trial designs.

This application takes advantage of the novel clinical trial design of the parent ABC study to directly address questions about how abatacept affects 1) naïve or memory T cell activation, 2) plasma cell survival, 3) regulatory T cell development and 4) regulatory B cell development and function. The CD28:CD80/CD86 interaction is crucial in regulating these immune processes, however understanding whether any or all of these mechanisms function to limit clinical disease activity and/or

systemic autoimmunity in human SLE (10), especially in patients where background immunosuppressants are not used, has not been investigated. We will address these critical issues through the following specific aims.

**Specific Aim 1: Determine if abatacept reduces the number of activated T cells in the peripheral blood in lupus patients.** *Hypothesis:* Since activation of naïve T cells requires CD80/CD86 engagement with CD28 on the T cell, blockade of this interaction by abatacept should reduce activated T cells in peripheral blood in patients responding to treatment with abatacept.

**Specific Aim 2: Evaluate if abatacept alters plasmablast survival in patients treated with abatacept.** *Hypothesis:* Interactions between plasmablasts expressing counter receptors for CD28 or CTLA4 are important for signaling survival of plasmablasts. Treatment with abatacept may reduce autoantibody producing plasmablasts in peripheral blood by blocking those signals.

**Specific Aim 3: Characterize regulatory T cell frequencies in lupus patients in abatacept treatment group compared to placebo group.** *Hypothesis:* T regulatory cell frequencies will be influenced by abatacept treatment of SLE patients and will help define which of the outcomes a) promote Treg development/ expansion or b) block Treg development leading to increased autoimmunity are observed clinically.

**Specific Aim 4: Determine whether abatacept treatment alters the development of IL-10 producing B regulatory cells.** *Hypothesis:* Abatacept interruption of CD28:CD80/CD86 interactions, which in lupus patients might be reducing Breg development or survival. This treatment may increase Breg frequencies and ability to better regulate autoimmune responses.

Note: Experimental approaches are summarized in the tables below and are more fully detailed in the full protocol submitted to NIH which is included with this protocol, along with the abatacept investigator brochure in the IRB submission package.

**Table 2: Single-cell proteomics: Intracellular cytokine**

**Table 1: Lyoplate Immunophenotyping PBMCS.**

[figure not shown]
[figure not shown]
Table X: Staining Profiles (Lyoplates)						Intracellular Staining Panels		
Fluorochrome	T cell	Treg	B cell/Breg	DC/mono/NK	Th1/2/17	Fluorochrome	T cell	B cell/Breg
FITC	PD-1	CD39	CD10	CD86	CXCR5	Pacific Orange	barcode	barcode
PE	CD197 (CCR7)	CD25	CD24	CD56	CXCR3	Alexa 750	barcode	barcode
PE-Texas Red	Live/dead	Live/dead	Live/dead	Live/dead	Live/dead	FITC	IFN-γ	CD10
PerCP-Cy5.5	CD4	CD4	CD19	CD123	CD4	PE	IL-17	CD24
PE-Cy7	CD45RA	CCR4	CD27	CD11c	CCR6	PE-Texas Red		IL-10
APC	CD38	CD127	CD38	CD16	CD38	PerCP-Cy5.5	CD4	CD19
Alexa 700	CD27		IgD	CD80		PE-Cy7	IL-2	CD27
APC-H7	CD8	CD45RO	CD20	CD3+19+20	CD8	APC	IL-4	CD38
V450	CD3	CD3	CD3	CD3	CD3	Alexa 700	TNFα	IgD
						APC-H7	CD8	TGFβ
							CD25	CD25

**Table 3:** Single-cell proteomics:  
Phosphoflow

B & T Cell Activation Phosphoflow Panel	
Fluorochrome	Biomarker
Pacific Orange	barcode
Alexa 750	barcode
Pacific Blue	CD3
PerCP-Cy5.5	CD4/CD20
Qdot 605	CD45RA
PE-Cy7	CD33
APC-H7	CD14/CD16 (dump)
FITC	p38 MAPK
PE	pPLC $\gamma$ 2

**Table 4:**

Functional Categories of 51-plex Bioplex200 Cytokine/Chemokine Panels		
Th1-like	Chemokine-Adhesion	Homeostasis
IL-12(p70)	IL-8/CXCL8	IL-7
IFN- $\gamma$	IP-10/CXCL10	IL-15
IL-2	RANTES/CCL5	
IL-2RA	MIP-1a/CCL3	Other
	MIP-1b/CCL4	LIF
	MCP-1/CCL2	PAI-1
	MCP-3/CCL7	PDGF-BB
	GRO $\alpha$ /CXCL1	Resistin
	SDF-1/CXCL12	Leptin
	MIG/CXCL9	SCF
	Eotaxin/CCL11	
Th17-like		ICAM-1
IL-17A		VCAM-1
IL-21		sE-selectin
IL-23		VEGF-A
IL-6		
Th2-like		
IL-4		BLyS**
IL-5		APRIL**
IL-13		sCD40L
		sFas
		sFasL
		TNF- $\alpha$
Regulatory	NGF/TNFR Superfamily	
IL-10		TNFR1 (p55)
TGF- $\beta$		TNFRII (p75)
		TRAIL
		NGF $\beta$
Innate		
IL-1 $\alpha$		
IL-1 $\beta$		
IL-1RA		
IFN- $\alpha$		
IFN- $\beta$		
G-CSF		

## Exploratory Clinical Assessments

Exploratory clinical endpoints will include:

Changes in CLASI, (cutaneous lupus endpoint)

LFA REAL (Rapid, Evaluation of Activity in Lupus)

Patient-reported outcomes: (LUPUS PRO and SF-36 domains)

These analyses will be performed according to the training on the LFA POINT website (Lupus Foundation of America Professional Online Instrument Training) which all investigators will be required to use for certification.

## 7 ADVERSE EVENT REPORTING

### 7.1 Adverse Events

An **Adverse Event (AE)** is defined as any new untoward medical occurrence or worsening of a pre-existing medical condition in a patient or clinical investigation subject administered an investigational (medicinal) product and that does not necessarily have a causal relationship with this treatment. An AE can therefore be any unfavorable and unintended sign (including an abnormal laboratory finding, for example), symptom, or disease temporally associated with the use of investigational product, whether or not considered related to the investigational product.

Adverse events can be spontaneously reported or elicited during open-ended questioning, examination, or evaluation of a subject. (In order to prevent reporting bias, subjects should not be questioned regarding the specific occurrence of one or more AEs.)

#### 7.11 Serious Adverse Events

A **Serious Adverse Event (SAE)** is any untoward medical occurrence that at any dose:

- results in death
- is life-threatening (defined as an event in which the subject was at risk of death at the time of the event; it does not refer to an event which hypothetically might have caused death if it were more severe)
- requires inpatient hospitalization or causes prolongation of existing hospitalization (see note below for exceptions)
- results in persistent or significant disability/incapacity
- is a congenital anomaly/birth defect
- is an important medical event, defined as a medical event that may not be immediately life-threatening or result in death or hospitalization but, based on appropriate medical and scientific judgment, may jeopardize the subject or may require intervention (eg, medical,

surgical) to prevent one of the other serious outcomes listed above. Examples of such events include but are not limited to intensive treatment in an emergency department or at home for allergic bronchospasm; blood dyscrasias or convulsions that do not result in hospitalization. Potential drug induced liver injury (DILI) is also considered an important medical event (see Section 7.6 for the definition of potential DILI).

Suspected transmission of an infectious agent (eg, any organism, virus or infectious particle, pathogenic or non-pathogenic) via the study drug is an SAE.

Although pregnancy, overdose and cancer are not always serious by regulatory definition, these events must be handled as SAEs (See Section 7.5 for reporting pregnancies).

**NOTE:** The following hospitalizations are not considered SAEs in BMS clinical studies:

- a visit to the emergency room or other hospital department lasting less than 24 hours that does not result in admission (unless considered an “important medical event” or a life-threatening event)
- elective surgery planned before signing consent
- admissions as per protocol for a planned medical/surgical procedure
- routine health assessment requiring admission for baseline/trending of health status (eg, routine colonoscopy)
- medical/surgical admission for purpose other than remedying ill health state that was planned before study entry. Appropriate documentation is required in these cases.
- admission encountered for another life circumstance that carries no bearing on health status and requires no medical/surgical intervention (eg, lack of housing, economic inadequacy, caregiver respite, family circumstances, administrative).

## **7.12 Nonserious Adverse Events:**

Nonserious adverse events are all adverse events that are not classified as SAEs.

## **7.13 Assignment of Adverse Event Intensity and Relationship to Abatacept**

All adverse events, including those that are serious, will be graded by the investigator as follows: **Mild (Grade 1):** awareness of event but easily tolerated, **Moderate (Grade 2):** discomfort enough to cause some interference with usual activity, **Severe (Grade 3):** inability to carry out usual activity, **Very Severe (Grade 4):** debilitating; significantly incapacitates subject despite symptomatic therapy.

The following categories and definitions of causal relationship to investigational product as determined by a physician should be used: **Related:** There is a reasonable causal relationship to investigational product administration and the adverse event. **Not Related:** There is not a reasonable causal relationship to investigational product administration and the adverse event.

The expression “reasonable causal relationship” is meant to convey in general that there are facts (eg, evidence such as de-challenge/re-challenge) or other arguments to suggest a positive causal relationship.

## **7.2 Collection and Reporting**

Adverse events can be spontaneously reported or elicited during open-ended questioning, examination, or evaluation of a subject. To prevent reporting bias, subjects should not be questioned regarding the specific occurrence of one or more adverse events.

If known, the diagnosis of the underlying illness or disorder should be recorded, rather than its individual symptoms. The following information should be captured for all AEs: onset, duration, intensity, seriousness, relationship to investigational product, action taken, and treatment required. If treatment for the event was administered, it should be recorded in the medical record. The investigator must supply BMS and the IRB/IEC with any additional information requested, notably for reported deaths of subjects.

### ***7.2.1 Serious Adverse Event Collecting and Reporting***

Following the subject's written consent to participate in the study, all SAEs, whether related or not related to study drug, must be collected, including those thought to be associated with protocol-specified procedures.

All SAEs must be collected that occur within 30 days of discontinuation of dosing. If applicable, SAEs must be collected that relate to any later protocol-specified procedure (eg, a follow-up skin biopsy).

The investigator should report any SAE occurring after these time periods that is believed to be related to study drug or protocol-specified procedure.

An SAE report should be completed for any event where doubt exists regarding its status of seriousness.

If the investigator believes that an SAE is not related to study drug, but is potentially related to the conditions of the study (such as withdrawal of previous therapy, or a complication of a study procedure), the relationship should be specified in the narrative section of the SAE Report Form.

All SAEs, whether related or unrelated to abatacept, and all pregnancies must be reported to BMS (by the investigator or designee) within 24 hours.

All SAEs should be reported via confirmed facsimile (fax) transmission, or scanned and reported via electronic mail to:

**SAE Email Address:** [contact]  
**SAE Fax Number:** <<[contact]>>

**All SAEs should simultaneously be faxed or e-mailed to BMS at:**  
**Global Pharmacovigilance & Epidemiology**

**Bristol-Myers Squibb Company**  
**[contact]**  
**Email: [contact]**

If an ongoing SAE changes in its intensity or relationship to study drug or if new information becomes available, a follow-up SAE report should be sent within 24 hours to the BMS using the same procedure used for transmitting the initial SAE report. All SAEs should be followed to resolution or stabilization.

### **7.2.2 Non-Serious Adverse Events (NSAEs) Collecting and Reporting**

The collection of non-serious adverse event (NSAE) information should begin at initiation of study drug. NSAE information should also be collected from the start of a placebo lead-in period or other observational period intended to establish a baseline status for the subjects. NSAEs should be followed to resolution or stabilization, or reported as SAEs if they become serious. Follow-up is also required for NSAEs that cause interruption or discontinuation of study drug, or those that are present at the end of study treatment as appropriate. All identified NSAEs must be documented appropriately.

Monitoring of Blood Draws: No more than 120 cc will be drawn at major PD visits (baseline, Month 3, Month 6) and no more than 60 cc will be drawn at interim visits (all others).

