## PROTOCOL SYNOPSIS

Protocol Title:	Clarification of Abatacept Effects in SLE with Integrated Biologic and Clinical Approaches (The ABC Study) The ABC Study:
Site Numbers/ Names:	Site 1: Oklahoma Medical Research Foundation
Research Hypothesis:	Abatacept is effective in lupus arthritis and this will be discernible in a small trial with robust endpoints which incorporates withdrawal of background immune suppressants
Study Schema: Drugs / Doses / Length of Treatment)	
 
1. Abatacept or placebo will be given in a 1:1 randomization subcutaneously q week for six months. Patients may elect to continue six more months on open label Abatacept.
 
2. Background Immune Suppressants will be withdrawn at any time between screening and the first dosing visit.
 
3. At or after screening, patients may elect 40-160 mg depomedrol shots prn not to exceed 320 mg total up to and including the Month 2 Visit (two months after the first dosing visit)
 
4. Additional steroids or immune suppressants, if necessary, will be allowed but the patient will be considered a non-responder on that basis
 
5. At the 3 month visit patients with significant clinical flare unresponsive to optional per protocol treatments may elect to receive open label Abatacept but will be considered non-responders in the primary endpoint at six months.
 

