## **Ethical Considerations:**

Integration of biologic discovery into clinical trials will generate data that might be used to help select more appropriate patient subsets for future trials and future treatment in clinic and to guide optimal dosing strategies. This is an ethical consideration since it could decrease the numbers of patients inappropriately exposed to a study medication in trials and in practice, and by allowing a better delineation of efficacy in the right population(s) this could also decrease the likelihood of widespread exposure in Phase III trials prior to acquiring sufficient data supporting potential efficacy.

The ethical basis of the current trial design has been debated widely in the lupus community. There is a realistic concern that withdrawal of background therapy will increase the risk of lupus flares and this trial design would be inappropriate for very ill patients such as those with active nephritis. However by decreasing the continued use of background immune suppressants which were obviously not working at the time of entry, by allowing steroid rescue and even restarting of meds as needed during the trial (defining such patients as non-responders) this design could be argued to be far more ethical than trials which legislate continuance of inadequate and potentially toxic background immune suppressant treatments for an entire year, with probable increase in risk for infections. In such protocols, patients who do not improve have only the choice of minimal rescue steroids or to drop out of the study, leading to unnecessary suffering which will not be required in this trial design. Finally, the concern about increasing flare risk should be somewhat alleviated by the results of the MMF, BOLD and Rontalizumab studies (all three of which have been completed using this trial design, and the latter presented at ACR 2012 (39)

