The study population will include patients between the ages of 18 and 70 who meet a minimum of 4 1997 revised ACR criteria for SLE and who present with a minimum of 3 tender and 3 swollen joints attributable to lupus arthritis. Patients may have other active manifestations of SLE, and, in the opinion of the investigator, they must be sick enough for intention to treat with a biologic and stable enough for this trial design, which includes withdrawal of any background immune suppressants, to be appropriate.

This study will enroll patients until 60 have completed the protocol through at least the six month point. Randomization will be 1:1 to abatacept or placebo. Approximately 30 patients are expected to complete each arm. At each visit history, physical, and blood tests appropriate to complete the outcome measures will be performed, and adverse event reporting and medication updates will be performed.

Subjects may continue to take nonsteroidal anti-inflammatory medications (including *prn* NSAIDS) and up to 20 mg prednisone (or oral steroid equivalent) daily during the study although steroids will be tapered as tolerated. If the patient is taking an immune suppressant (e.g. antimalarials, mycophenolate mofetil, azathioprine, leflunomide, methotrexate, a calcineurin inhibitor or belimumab) at screening, this must be stopped prior to or on the day of the baseline visit. Patients can elect to receive one or more depomedrol injection(s) up to a total of 320 mg total at the time of the screening visit and/or up to and including the Month 2 visit. Daily oral steroids will be tapered as tolerated if and when the patient begins to improve.

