**6) Prohibited Treatments and/or Therapies**

- a) Subjects who have at any time received treatment with any investigational drug within 28 days (or less than 5 terminal half-lives of elimination) of the Day 1 dose.
- b) Subjects who have received cyclophosphamide within 3 months of the Day 1 dose or bolus parenteral steroids  $\geq$  500 mg within 1 month of screening.
- c) Ongoing treatment (after the baseline visit) with immune suppressants (such as antimalarials, methotrexate, azathioprine, mycophenolate mofetil, leflunomide, calcineurin inhibitors or belimumab) after the baseline visit. These may be stopped or tapered as soon as informed consent procedures have been completed at the screening visit.
- d) Prednisone  $> 20$  mg po qd at the time of the screening visit (steroids will additionally be tapered during the study if possible at the discretion of the investigator). The exception to this are the protocol-allowed Depomedrol shots which will be used for rescue if needed. A total of 320 mg of intramuscular depomedrol can be given in increments of 40-160 mg at any time from the Screening Visit (after informed consent is signed and blood drawn) until the end of the Month 2 Visit (after blood drawn) If subjects remain on prednisone, no dose increases will be allowed during the study.

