**TIME AND EVENTS SCHEDULE: PROTOCOL IM101-345**

Procedure	Screening Visit	Treatment Visit 1 1 st Dosing	Treatment Visit 2-7 Month 1-6	Follow up Visits post-Rx	Visits 8-13 Month 7-12
Eligibility Assessments					
Informed Consent	X*				
Inclusion/Exclusion Criteria	X	X			
Medical History	X	X	X	X	X
Safety Assessments					
Medication List	X	X	X	X	X
History, Vital Signs, Physical Examination	X	X	X	X	X
Adverse Events Assessment		X	X	X	X
Clinical Laboratory Tests	X	X	X	X	X
PK sampling	X**	X**	X**		X**
Immunogenicity	X***	X***	X***		X***
PD sampling	X****	X****	X****		X****
Pregnancy Test	X	X	X	X	X
Efficacy Assessments					
SLEDAI/SSFI/PGA	X	X	X	X	X
BILAG 2004	X	X	X	X	X
CLASI	X	X	X	X	X
DIAL	X	X	X	X	X
Patient Questionnaires (SF-36, LupusPRO)	X	X	X	X	X
Clinical Drug Supplies					
Randomize		X			
Dispense Study Treatment baseline and q month		X	X		X

\*Repeated for protocol amendments or new safety data

\*\* Screening, Months 1,2, 3,4, 6, 7,8, and 12 and/or EOS (if patients withdraw early)

\*\*\*Screening, Months 1,2, 6, 7, 8, 12 and/or EOS

\*\*\*\* At Screening Visit, first dosing, visits 3, 6, 9 and 12 and/or EOS (</= 160 cc blood, up to 30cc urine, up to 10cc saliva)

Non PD visits are restricted to </= 80 cc blood, up to 30 cc urine, up to 10 cc saliva)

Note that PK/PI/PD labs at screening should be drawn at the screening visit if possible, otherwise may be drawn anytime up to and including the First Dosing Visit, but must be draw prior to receiving any steroid injection(s) in the protocol.

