## 9. Statistical Considerations

**Enrollment is expected to include at least 70 screened and 60 randomized subjects** subjects have either reached a six month endpoint and/or been defined as a permanent non-responder for off protocol treatment or by dropping out of the protocol.

**The primary endpoint is the proportion of placebo vs treatment subjects who meet the primary endpoint of BICLA response using Chi Square analysis at month 6 as determined by an intent to treat analysis**

Subjects who drop out prematurely for any reason or are treated with off protocol medications or cross over to open label for lack of response at Month 3-6 are considered non responders at month 6.

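### Non-serious adverse events are not clearly required to be collected before the first dose, although immune suppressants may be stopped and depomedrol given from screening

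*Combined protocol and SAP*

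**What the plan says.** **When the protocol's interventions start.** The Synopsis states: "Background Immune Suppressants will be withdrawn at any time between screening and the first dosing visit". Section 4.2.2, item 6c, on the same drugs: "These may be stopped or tapered as soon as informed consent procedures have been completed at the screening visit". Section 4.1 sets the latest point: "this must be stopped prior to or on the day of the baseline visit". Optional depomedrol may also be given from the screening visit, after consent and the blood draw (Section 4.2.2, item 6d). Section 6.1 brings qualified subjects back within one month for randomisation and first dosing. Section 6.3.2 allows screening to be extended, with no stated maximum, when cancer screening is suspicious. Section 4.1 notes that some eligibility criteria await blood results.

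**When adverse events are collected.** Section 7.2.2: "The collection of non-serious adverse event (NSAE) information should begin at initiation of study drug". The next sentence adds: "NSAE information should also be collected from the start of a placebo lead-in period or other observational period intended to establish a baseline status". In the Time and Events Schedule, the row "Adverse Events Assessment" is empty under Screening and first marked at Treatment Visit 1. Section 7.1 defines an adverse event in a subject given an investigational product, and Section 5.1 classes depomedrol as non-investigational. Serious events are collected from written consent, and Section 7.2.1 asks that those possibly related to withdrawal of earlier therapy be identified as such.

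**What the protocol says about the risk.** Ethical Considerations: "There is a realistic concern that withdrawal of background therapy will increase the risk of lupus flares".

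**The concern.** The first things this trial does to a patient can come before study drug: stopping an immune suppressant and injecting a steroid. The rule for non-serious events is anchored to study drug instead. A non-serious infection, steroid reaction or withdrawal effect after screening but before Day 1 therefore has no clear place in the record. A consented patient who stops treatment and then proves ineligible is offered a visit to discuss other care (Section 4.1), and the schedule gives that patient no adverse event assessment.

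This matters because the protocol names flare after withdrawal as a realistic concern, and Section 1.6 presents the trial as proof of concept for the feasibility of this kind of design. Readers will take from it how well withdrawal was tolerated. If early non-serious events and patients who never reach dosing are missing, that description would be incomplete in the favourable direction. The quarterly adverse event reports to the DSMB would share the gap.

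**Working it through.** The plan states no figure for this point. The check sets the timing rules side by side and then sizes the interval.

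**1. Length of the interval in randomised patients.**
- Shortest: immune suppressants stopped on the baseline day and no depomedrol at screening, so 0 months.
- Longest under the usual rule: drugs stopped or depomedrol given at screening, with first dosing one month later, so 1 month. It is longer if screening is extended under Section 6.3.2.
- As a share of the time from consent to Month 6: 1 / (1 + 6) = 1/7, about 14%. This is the ceiling under the one-month rule, not an expected value.

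**2. Patients consented but never randomised.** Section 9 says: "Enrollment is expected to include at least 70 screened and 60 randomized subjects".
- 70 − 60 = 10 patients, and 10/70 = 14.3% of those screened.
- The documents do not say how many of these would have stopped a drug or received depomedrol. The range is 0 to 10.
- The count is approximate: 70 is a minimum, and the Synopsis and Section 4.1 recruit until 60 patients have completed Month 6, so both numbers may be larger.

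**3. Coverage between consent and first dose.**

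| Type of event | Randomised patients | Consented, never dosed |
|---|---|---|
| Serious | Collected from consent (6.3, 7.2.1) | Collected from consent |
| Lupus worsening | Scored by SLEDAI and BILAG at Treatment Visit 1 | No scheduled visit after screening |
| Non-serious infection, steroid reaction, other withdrawal effect | Not clearly required: 7.2.2 starts at study drug | Not clearly required; no scheduled assessment |

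**4. Does the second sentence of 7.2.2 close the gap?** It extends collection to a placebo lead-in or to another observational period that establishes baseline status. This trial has no placebo lead-in. Whether a screening period with active withdrawal and steroid injection counts as observational is not stated anywhere. If it does, the schedule should show collection from screening, or say that the Treatment Visit 1 assessment looks back to consent; it does neither. If it does not, the events fall outside collection. Both readings need the same clarification.

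**5. Effect on the comparison of arms.** The interval ends at randomisation, so under-recording in it should fall on both arms alike.

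**The case against.** A reader might infer that non-serious events are collected only from the first dose, so that harms of withdrawal go unrecorded for a month and altogether in screen failures. The documents do not support that much, for these reasons.

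- The observational-period sentence can be read to cover screening, where baseline samples and measures are taken. The text is ambiguous; it does not plainly exclude these events.
- Treatment Visit 1 has an adverse event assessment, a medication list, an examination and laboratory tests. SLEDAI looks back 28 days and BILAG 4 weeks, nearly the whole one-month window.
- Section 8 sends flare data to the DSMB whatever the attribution. Section 7.7 requires significant worsening on examination to be recorded as an adverse event, and Section 7.3 covers clinically significant laboratory results.
- Serious events, including important medical events, run from consent in screen failures too.
- Early withdrawal and depomedrol are permitted at screening, not required, and events they cause arise after that visit. A mark in the screening cell alone would add little.
- Section 4.1 encourages follow-up at 2 and 4 months for patients who withdraw for any reason.
- Safety analysis is descriptive (Section 9.4.2), and estimating the safety of withdrawal is not a listed objective.

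Most of this stands and narrows the point to non-serious events and to unclear wording. It does not remove it. Lupus indices do not record infections or steroid reactions. The Synopsis treats Day 1 as the baseline visit, so earlier worsening can be absorbed into baseline. Section 8 gives no start date for flare reporting and does not mention patients never randomised. Section 6.3 confines safety evaluation to dosed subjects, and the follow-up rules in 4.2.3 apply to those who discontinue investigational product.

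**Conclusion.** The point holds in a limited form. No section clearly requires non-serious events to be collected between the start of withdrawal or depomedrol and the first dose, or in consented patients who are never dosed, and Section 7.2.2 and the schedule do not agree on whether screening is covered. The interval is 0 to 1 month per randomised patient, longer if screening is extended. The number of never-randomised patients affected is not stated; it is roughly 0 to 10, assuming 70 screened and 60 randomised.

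The consequence is for the absolute description of how safe the withdrawal design is and for what the DSMB sees. It would be wrong to infer a biased safety comparison between abatacept and placebo, because the interval precedes randomisation. It would also be wrong to treat 14% of exposure or 10 patients as expected losses; both are ceilings under the stated assumptions. This is an inexpensive improvement to data collection.

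**What to change.** - Section 7.2.2: start collection of non-serious events at consent, matching serious events, and replace the observational-period sentence with a plain statement that screening is included.
- Section 7.1: extend the adverse event definition to events after protocol-directed withdrawal and after depomedrol.
- Time and Events Schedule: state that the Treatment Visit 1 assessment covers the interval since consent.
- Consented patients never randomised: apply the same rule up to the visit at which alternative care is discussed.
- Sections 8 and 9.4.2: tabulate pre-dose events separately, including those in patients never dosed, and include them in the quarterly DSMB report.

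None of this changes a treatment or a clinical rule. Staff already see randomised patients at Treatment Visit 1, and the protocol already provides the visit for ineligible ones. The cost is protocol wording, a few more adverse event records and one more table.
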